#### Table 9-2: Summary of mTPI-2 Performance

	mTPI-2
Probability of Selecting the MTD	0.712±0.223
Probability of Toxicity	0.318±0.199
Probability of Selecting Dose-over-MTD	0.031±0.04
Probability of No Selection	$0.167 \pm 0.408$

MTD=maximum tolerated dose; mTPI-2=Modified Toxicity Probability Interval Design No 2

# 9.2 Sample Size Determination

### Sample Size Determination Phase 1:

A maximum of 36 patients will be used for each Phase 1 dose escalation component (single agent and combination therapy). The total number of patients included across all cohorts in the Phase 1 dose escalation and enrichment parts will be approximately 150.

### Phase 2:

The initial Phase 2 dose assessment part in one or more specific indication(s) (see Section 3.1.4) will include approximately 20 patients (ie, 15 anti-PD-(L)1 naïve and where feasible five anti-PD-(L)1 pre-treated patients) at each of two dose levels of KY1044 (as single agent or in combination with atezolizumab).

Once the RP2D is established, Phase 2 may be extended and approximately 15 patients will be enrolled initially in each tumor type in the anti-PD-(L)1 naïve subgroup per each indication in either the single agent cohort or the combination cohort.

The full sample size of specific indications in Phase 2 of the study will be based on early evaluation of ORRs and only indications with promising response rates will be expanded further (up to 40 per subgroup). The Go-no-go decision criteria for cohort expansion will be based on historical ORR rates and a target ORR response rate for KY1044 treatment. No formal statistical testing will be performed. Instead, confidence intervals will be constructed around the objective response rate observed in each cohort, and this will enable decisions to be made around the likely success of future studies.

Historical response rates for monotherapy with ICI in the second line metastatic setting are in the region of 15% to 25% for anti-PD-(L)1 inhibitors as monotherapy across the different indications and will be even lower in more advanced stages of disease ( $\geq$ 3 lines of anti-cancer treatment in the metastatic setting).

In order to illustrate the impact of sample sizes of 15 or expansion to 40 on the width of the confidence intervals, example evaluations are given for these 3 situations (ORR of 13% (3 and more lines of prior therapies in the advanced metastatic setting and 20% and 33% ORR for  $2^{nd}$  line metastatic setting) for cohort sizes of either 15 or 30 patients are given below:

- If the observed response rate is 13% (2/15), the 2-sided 80% confidence interval will be (4%, 32%).
- If the observed response rate is 20% (3/15), the 2-sided 80% confidence interval will be (8%, 39%).
- If the observed response rate is 33% (5/15), the 2-sided 80% confidence interval will be (17%, 53%).

Property of the Sanofi Group - strictly confidential

- If the observed response rate is 13% (5/40), the 2-sided 80% confidence interval will be (6%, 22%).
- If the observed response rate is 20% (8/40), the 2-sided 80% confidence interval will be (12%, 30%).
- If the observed response rate is 33% (13/40), the 2-sided 80% confidence interval will be (23%, 44%).

In the anti-PD-(L)1 pre-treated subgroup, initially up to 10 patients will be recruited in each indication in either the single agent cohort or the combination cohort. These patients will have already progressed on previous immunotherapy; hence any individual response would indicate a proof of mechanism in these patient groups. If signs of efficacy have been observed in at least one patient any of these anti-PD-(L)1 pre-treated indications a further expansion up to 40 patients per cohort will be considered.

This number of patients, also offers the opportunity to evaluate further the safety and PK/PD of the chosen MTD/RP2D of KY1044 as single agent or in combination with atezolizumab.

Overall a maximum of 412 patients may be enrolled into the study (Phase 1 and 2).

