#### **Optional Phase 1 enrichment part**

An optional enrichment part may include the testing of additional patients at one or more dose levels to better understand the safety, tolerability, PK, preliminary anti-tumor efficacy and/or PK/PD relationships of KY1044 as single agent and/or in combination with atezolizumab.

The enrichment part of the study will only use doses that have already been explored in the Phase 1 dose escalation parts of the study, and have been determined to be safe.

# Total number of patients in Phase 1

The total number of patients included across all cohorts in the Phase 1 dose escalation and enrichment parts will be approximately 150.

# 3.1.4 Phase 2

In the absence of identifying an MTD or single efficacious dose in Phase 1, an initial Phase 2 dose assessment part in one or more specific indication(s) will be opened to compare the efficacy and biomarker readouts of two biologically relevant dose levels of KY1044 (as single agent or in combination with atezolizumab) in a more homogeneous population. Up to

20 patients (ie, 15 anti-PD-(L)1 naïve patients and where feasible five anti-PD-(L)1 pre-treated patients) will be included at each dose level and indication. Together with safety, efficacy and biomarker data from Phase 1, data from this part will assist with the selection of the RP2D. Once the MTD and/or RP2D has been identified, Phase 2 may be extended to explore efficacy at the RP2D in additional selected indications as described below.

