### 5.9 Patient Numbering and Treatment Assignment

Patients will be assigned to two treatments groups in this study, KY1044 as single agent or in combination with atezolizumab in an open-label manner. Allocation of the IMP kits during the study period will be done via IXRS.

**Phase 1:** The assignment of a patient to a particular cohort during the Phase 1 dose escalation or enrichment components (KY1044 as single agent or in combination with atezolizumab) will be coordinated in IXRS in accordance with the Cohort Management Plan.

Patients will be identified with unique patient numbers assigned by IXRS at the time of screening and then at enrolment. Enrolment number will start with the digit "1" indicating that the patient is being treated in Phase 1 of the study, in addition to a digit indicating a cohort to which the patient was allocated and an arm of treatment (KY1044 single agent or in combination with atezolizumab). Enrolment number will identify the patient in all study databases including eCRF, central laboratory, central imaging and ECG and will be linked to the patient's name in an identification list retained in the Investigator's Site File.

**Phase 2:** The assignment of a patient to a particular group during the Phase 2 will be based on tumor indication and history of anti-PD-(L)1 treatment (Figure 3-1). In the initial Phase 2 dose assessment part, two biologically relevant dose levels of KY1044 (as single agent or in combination with atezolizumab) that have been determined to be safe in Phase 1 will be explored in one or more indication(s). In the Phase 2 expansion component, patients will receive the RP2D of KY1044 as single agent or in combination with atezolizumab that was established during the Phase 1 dose escalation and/or enrichment component and/or the initial Phase 2 dose assessment part of the study.

Patients will be identified with unique subject numbers assigned by IXRS at the time of screening and then at enrolment. Enrolment number will start with the digit "2" indicating that the patient is being treated in Phase 2 of the study, in addition to a digit indicating an arm of treatment (KY1044 single agent or in combination with atezolizumab). Enrolment number will identify the patient in all study databases including eCRF, central laboratory, central imaging and ECG and will be linked to the patient's name in an identification list retained in the Investigator's Site File.

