6.3 Randomization and Blinding

Not applicable. This is an open-label study without randomization.

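### The Phase 2 dose-assessment part compares two KY1044 doses with no rule for who receives which dose, so the comparison is open to avoidable allocation bias

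*Protocol*

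**What the plan says.** Protocol 3.1.4 opens the initial Phase 2 dose-assessment part when Phase 1 has found neither an MTD nor a single efficacious dose. (Protocol 3.1 mentions the part without that condition.) Its purpose is "to compare the efficacy and biomarker readouts of two biologically relevant dose levels of KY1044", and "data from this part will assist with the selection of the RP2D", alongside Phase 1 safety, efficacy and biomarker data.

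Protocol 9.2 sets the size at about 20 patients "at each of two dose levels of KY1044 (as single agent or in combination with atezolizumab"), made up of "15 anti-PD-(L)1 naïve and where feasible five anti-PD-(L)1 pre-treated patients".

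On allocation, Protocol 5.9 says: "The assignment of a patient to a particular group during the Phase 2 will be based on tumor indication and history of anti-PD-(L)1 treatment". The same section mentions the two doses but gives no rule for choosing between them, and it cites the Cohort Management Plan for Phase 1 only. SAP 6.3 reads: "Not applicable. This is an open-label study without randomization".

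On analysis, SAP 10.0 limits the statistics to descriptive summaries and reports Phase 2 by indication, anti-PD-(L)1 group and, as appropriate, dose level. SAP 10.5.2.3 and 10.5.2.4 plan no sensitivity or supplementary analyses.

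**The concern.** This part has a stated purpose of comparing two groups within the trial. Indication and anti-PD-(L)1 status are held fixed. Number of prior lines, PD-L1 status, ECOG, site and calendar time are not. The text also does not require the two doses to enrol at the same time. Filling one dose before the other, or giving different sites different doses, would be compatible with what is written.

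The protocol itself treats one of these factors as prognostic. Section 9.2 expects lower response rates after three or more lines than in second line. If the two dose groups differ in that respect, part of the observed difference reflects who was enrolled, and the planned analysis does not separate that from a dose effect. The result then contributes to the RP2D used in the expansion cohorts. Response is assessed by the investigator in an open-label study, so there is no independent check unless the sponsor takes up the optional central review.

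**Working it through.** **1. The plan's own figures.** The only Phase 2 precision figures are the exact two-sided 80% intervals in Protocol 9.2. Clopper-Pearson limits (beta quantiles at 0.10 and 0.90) give:

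- n = 15: 2/15 gives 3.6% to 31.7%; 3/15 gives 7.6% to 39.3%; 5/15 gives 17.2% to 53.2%.
- n = 40: 5/40 gives 6.2% to 22.0%; 8/40 gives 12.0% to 30.4%; 13/40 gives 22.7% to 43.8%.

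All six agree with the protocol after rounding. They describe single cohorts. No figure is given for the difference between doses.

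**2. Inputs for the illustration.**

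- 15 naïve patients per dose (Protocol 9.2).
- ORR of 13% after three or more lines (Protocol 9.2 example).
- Second-line ORR of 20% or 33% (Protocol 9.2 examples), and 25%, the top of the 15% to 25% historical range in the same section.
- Second-line share of 75% at one dose and 25% at the other. This is an assumption; the documents give no mix.
- No dose effect.

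**3. Expected ORR by dose.** Expected ORR = (second-line share × second-line ORR) + (remaining share × 13%).

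- Second-line ORR 20%: 0.75 × 20 + 0.25 × 13 = 18.25%; 0.25 × 20 + 0.75 × 13 = 14.75%. False difference 3.5 points.
- Second-line ORR 25%: 18.75 + 3.25 = 22%; 6.25 + 9.75 = 16%. False difference 6 points.
- Second-line ORR 33%: 24.75 + 3.25 = 28%; 8.25 + 9.75 = 18%. False difference 10 points.

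**4. Which dose appears better.** Let X1 and X2 be independent binomials with n = 15 and the rates above. Summing the joint probabilities exactly gives:

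| Second-line ORR | Rates compared | Better-mix dose leads | Tie | Other dose leads |
|---|---|---|---|---|
| 20% | 18.25% v 14.75% | 50.4% | 19.1% | 30.5% |
| 25% | 22% v 16% | 57.4% | 17.1% | 25.5% |
| 33% | 28% v 18% | 67.0% | 14.0% | 18.9% |

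With a 50/50 mix at both doses, each dose leads in 40.1% (common rate 16.5%), 40.7% (19%) or 41.4% (23%) of trials.

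**5. What randomisation would and would not change.** The expected case-mix difference becomes zero. Chance imbalance remains: if half the patients are second line (assumption), the two groups of 15 differ by 6 or more second-line patients (40 points) with probability 4.3%, and by 8 or more with probability 0.5%. Precision stays the same. Power for 20% against 33% with 15 per dose is 12% at two-sided 5% and 32% at two-sided 20%. An observed 5/15 against 2/15 has a 95% interval for the difference of about −11 to +47 points.

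**The case against.** The strongest reply is that little rests on this comparison alone. The part is conditional under Protocol 3.1.4. Protocol 5.4.7 makes the RP2D a joint judgement on safety, exposure, target occupancy, PK/PD and activity. No test is planned, and with 15 per dose the comparison is imprecise however patients are allocated. This stands, and it limits the severity. It does not justify leaving a removable bias in a comparison that will still be read.

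The confounder in the illustration is also partly controlled. Protocol 4.2 limits combination patients with NSCLC or HNSCC to one or two prior lines, which on a plain reading excludes the 13% stratum. This stands for those cohorts. No limit is written for gastric/esophageal or cervical cancer, for indications admitted on Phase 1 activity, for TNBC or for single-agent patients. The other uncontrolled factors remain in every cohort.

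Third, the figures depend on inputs chosen for illustration. Protocol 9.2 uses 13%, 20% and 33% to show interval widths, not to estimate an effect of treatment line, and 33% lies above its own historical range. A 75/25 split would rarely arise by chance and so implies systematic channelling, for which the documents give no evidence. All of this stands, which is why a range is shown.

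Finally, SAP 10.0 already allows reporting by dose level, and SAP 10.2 summarises ECOG, tumour history and prior anti-cancer therapies. Some imbalance would therefore be visible, though not prevented or adjusted for. PD-L1 is an exploratory endpoint and is not in that baseline list.

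**Conclusion.** The point holds as a design weakness. The documents plan a comparison of two doses, give no rule for assigning dose, and rule out randomisation. The comparison is therefore open to confounding by prior lines (less so for NSCLC and HNSCC combination patients), PD-L1 status, ECOG, site and calendar time.

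Under the assumed 75/25 mix and no dose effect, the false difference is 3.5 to 10 points. The better-mix dose leads in 50.4% to 67.0% of trials, against 40% to 41% with equal mix. Within the protocol's historical second-line range the relevant figures are those at 20% and 25%, namely 50.4% and 57.4%.

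A reader might infer that the comparison is confounded, or that case mix alone could select the RP2D. The documents support neither. Imbalance is possible but cannot be known in advance, and the RP2D draws on several other sources. The study design figure, to which Protocol 5.9 refers for Phase 2 assignment, is not in the text available here. SAP 6.3 is nonetheless explicit about randomisation. The matter is a worthwhile, inexpensive improvement rather than a mandatory correction.

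**What to change.** In Protocol 5.9 and 9.2 and in SAP 6.3, state that while both dose levels of the dose-assessment part are open, the IXRS allocates patients 1:1 at random between them, within indication and anti-PD-(L)1 status, with treatment remaining open-label. In SAP 10.0, present this part by randomised dose and tabulate number of prior lines and PD-L1 status by dose.

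The SAP's document history dates version 3.0 to March 2024, so some patients may already have been allocated. New wording cannot change that. For them, label the dose comparison as non-randomised and give the same table by dose.

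The cost is protocol and SAP wording plus an IXRS allocation list. The IXRS already numbers patients and allocates kits, and the target size is already the same at each dose. No extra patients or procedures are needed. The downside is that both doses must be open at the same time. Randomising removes the expected allocation bias but does not narrow any interval, so the result should still be read as an estimate.

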# 9.3 Analysis Set

#### 9.3.1 Full Analysis Set

The full analysis set (FAS) will consist of all patients who are allocated to study drug, regardless of treatment ultimately received. The FAS will generally be the primary population of interest for efficacy endpoints.

#### 9.3.2 Safety Set

The safety set will consist of all patients who take at least one dose of study drug.

Any additional analysis sets will be defined in the Statistical Analysis Plan (SAP).

### 9.4 Statistical Analyses

Full details of the statistical analyses of the data will be documented in an agreed SAP, which will be finalized prior to locking the database. There will be a preliminary analysis of the study data according to the requirements defined in Section 3.5. Final data analysis will be performed at the end of the study.

Phase 1 will be reported by dose group(s) within KY1044 single agent and KY1044 combination groups.

Phase 2 of the study will be reported by indication and dose group(s) within KY1044 single agent and KY1044 combination groups, split by anti-PD-(L)1 naïve and pre-treated groups.

Wherever possible, patients with the same tumor type who have received the recommended dose(s)/schedule(s) of KY1044 as single agent or in combination with atezolizumab will be pooled for analysis.

In general, continuous variables will be summarized by number of patients, mean, standard deviation (StD), median, and minimum, maximum. Categorical variables will be summarized by frequency counts and percentages.

### 9.4.1 Demographic and Baseline Characteristics

Demographic variables (age, gender and race), medical history, physical examination and ECOG performance status will be summarized. Body weight, height and BMI will also be summarized.

#### 9.4.2 Efficacy Analysis

#### 9.4.2.1 Analysis of Primary Endpoints

The primary endpoint in Phase 2 is ORR per RECIST 1.1. ORR will be assessed using descriptive statistics for categorical data by indication along with the associated 2-sided exact 80% and 95% CIs. The primary endpoints in Phase 1 are safety endpoints (see Section 9.4.3).

#### 9.4.2.2 Secondary Analysis of Secondary Endpoints

Secondary efficacy endpoints include:

- ORR per RECIST 1.1 (Phase 1 only)
- ORR and PFS per iRECIST (Phase 1 and Phase 2)
- Best Overall Response (BOR), PFS and DOR per RECIST 1.1
- Survival rate at 12 and 24 months

Response endpoints will be summarized using descriptive statistics for categorical data by treatment group along with the associated 2-sided exact 95% CIs.

Time-to-event endpoints (eg, DOR, PFS) will be summarized using the Kaplan-Meier method and displayed graphically where appropriate. Median event times and 2-sided 95% confidence interval for each median will be provided. For survival rate at 12 and 24 months, Kaplan-Meier estimates with 95% CIs will be presented.

Pharmacodynamic endpoints include:

- Presence and/or concentration of anti-KY1044 and anti-atezolizumab antibodies
- Presence of TILs as determined by expression of ICOS, FOXP3 and CD8 cells (IHC)

Continuous endpoints, eg, the concentration of anti-KY1044 and anti-atezolizumab antibodies will be summarized using summary statistics, number of patients (n), mean, StD, median, minimum and maximum values.

Categorical endpoints, eg, Presence of anti-KY1044 and anti-atezolizumab antibodies will be summarized using frequency counts and percentages.

The association between expression of ICOS and other immunological markers with efficacy endpoints will be explored graphically.

#### 9.4.2.3 Analysis of Exploratory Endpoints

The following exploratory endpoints will be evaluated using summary statistics and frequency counts as applicable. Full details of exploratory analyses including graphical presentations will be described in the Statistical Analysis Plan.

• Expression of immune- and response-related markers such as (but not limited to) PD-L1, CD163, CD68 by IHC

- mRNA gene signature (transcriptomics/ Nanostring) with special interest in IFN gene signature (PanInflammatory panel and/or IO360 panel)
- Peripheral, soluble ligands and cytokine levels (eg, IFNγ, TNFα, GM-CSF) contingent on availability of assay (ie, SIMOA)
- Phenotype and markers of IC activation in peripheral blood (eg, CD3, CD8, CD4, TRegs, CD4 memory cells, CD25, FOXP3, CD45RA, ICOS, CD14. CD45, CD56, CD19 and ICOSLG) (FACS or ChipCytometry)
- PBMCs gene signature (RNA) (transcriptomics Nanostring)
- ICOS Receptor Occupancy (RO) in PBMCs (KY1044 as single agent in Phase 1 only)

#### 9.4.3 Safety Analysis

The Phase 1 primary and Phase 2 secondary safety endpoints include:

- Safety: Incidence and severity of AEs and SAEs, including changes in laboratory parameters, vital signs and ECGs
- Tolerability: Dose interruptions, reductions and dose intensity

For Phase 1, the primary endpoints will also include:

- The incidence of DLTs with KY1044 as single agent during the first 21 days of treatment
- The incidence of DLTs with KY1044 in combination with atezolizumab during the first 21 days of treatment

All AEs in the clinical trial database will be coded according to the Medical Dictionary for Regulatory Activities (MedDRA) Version 21.0 or higher, which will be used to summarize AEs by primary system organ class (SOC) and preferred term (PT). All AEs will be displayed in listings.

A treatment emergent adverse event (TEAE) is defined as an AE observed after starting administration of the specific treatment. If a patient experiences an event both prior to and after starting administration of a treatment, the event will be considered a TEAE (of the treatment) only if it has worsened in severity (ie, it is reported with a new start date) after starting administration of the specific treatment, and prior to the start of another treatment, if any. All TEAEs collected during the investigational period will be summarized.

Treatment-related AEs/SAEs coded by primary SOC and PT will be summarized in those receiving at least one infusion of KY1044.

Additional summaries by severity of AEs/SAEs will also be produced.

Actual and change from baseline data for vital signs and ECG parameters will be reported using summary statistics.

When relevant, for laboratory variables, descriptive statistics for results and changes from baseline will be provided during the on-treatment period. These analyses will be performed using local measurements for laboratory variables. Clinical laboratory results will be graded according to NCI CTCAE version 5.0, when applicable. Number (%) of participants with laboratory abnormalities (all grades and by grade) using the worst grade during on-treatment period will be provided for the all-treated population.

When the NCI CTCAE version 5.0 scale is not applicable, the number of participants with laboratory abnormality out-of-normal laboratory range value will be displayed.

The number of dose interruption, reductions and incidence of DLTs will be summarized.

Continuous endpoints, will be summarized using summary statistics, number of patients (n), mean, StD, median, minimum and maximum values.

Categorical endpoints, will be summarized using frequency counts and percentages.

#### 9.4.4 Pharmacokinetic Analysis

The serum PK of KY1044 as a single agent, in combination with atezolizumab and for atezolizumab alone will be characterized using no compartmental analysis. The following PK measures will be calculated, whenever possible, from serum concentrations:

- Cmax: Maximum concentration (for atezolizumab only one timepoint of serum concentration at the end of infusion)
- tmax: Time of the maximum concentration (obtained without interpolation)
- Cmin: Trough concentrations
- $\lambda z$ : Terminal elimination rate constant (whenever possible)
- AUC0-last: Area under the concentration-time curve calculated using
- Linear trapezoidal summation from time 0 to time last, where "last" is the time of
- The last measurable concentration
- AUC0-inf: Area under the concentration-time curve from 0 to infinity,
- Calculated using the formula:  $AUC_{0-inf} = AUC_{0-last} + C_{last} / \lambda z$ , where  $\lambda z$  is the apparent terminal elimination rate constant
- Clearance
- Volumes of distribution
- t1/2: Half-life

For both KY1044 and atezolizumab, all peak (end-of-infusion) and trough (pre-infusion) concentrations will be tabulated. For KY1044 peak and trough concentrations will be tabulated separately for use as a single agent and for combination with atezolizumab.

Besides listings of pharmacokinetic measures for individual patients, all measures will be summarized. The summaries will include estimates of not only central tendency but variability such as Standard Error. For concentrations, geomeans will be provided. For  $t_{max}$  median (and range) and for half-lives, arithmetic means will be provided. Besides listings of concentrations, noncompartmental analysis (NCA) tables, charts illustrating the concentration-time profiles will be generated.

Additional pharmacokinetic analyses may be undertaken. For instance, if the tables of peak and trough concentration (or anti-drug antibody) indicate some kind of interaction between KY1044 and atezolizumab, pharmacokinetic modelling of these data may be undertaken. Exploratory analyses may also be conducted to estimate dose proportionality and accumulation ratio on relevant parameters.

Population PK analysis may be performed if deemed relevant and applicable, and the results will be summarized in a stand-alone report if deemed relevant. In this context, further exposure-response analyses may also be conducted.

